2.1 Study Flow Charts

[figure not shown]

Figure 1: Recruitment, Screening and Intervention Preparation flow chart. Note that the ultrasound screening session can optionally be consented for in advance of the main study consent.

[figure not shown]

Figure 2: Part I Intervention Plan, Recovery & Follow-up flow chart

[figure not shown]

Figure 3: Part II Intervention Plan, Recovery & Follow-up flow chart

2.2 Duration of patient participation

Participants will be in the study for less than three months following entry on study and the participant will be followed up clinically for a maximum of 37 days and radiologically for a maximum of 60 days after intervention (Day 1).

2.3 Post-trial care and follow-up

Following the completion of the study, patients will receive standard care until disease progression or death.

3 OBJECTIVES AND ENDPOINTS

The objectives and endpoints for the study are detailed in the following tables. Only evaluable samples will be included in endpoint analysis. All endpoints will be evaluated at the end of Phase II.

The following qualifiers (*, †, ‡ and §) apply to Table 1, Table 2 and Table 3:

* In Part II the Unreleased biopsy is not performed and therefore the average value for all evaluable tumours receiving intervention in Part I is used as a comparison for the two-fold increase from Unreleased to Released biopsy.

† Duration refers to the completion of sample processing but not necessarily the sample analysis. The sample may be stored in a fixed or frozen state and analysed at some time period beyond the specified duration, for example to facilitate batch processing.

‡ Analytical method will only be performed where tissue mass allows. It is expected at most one technique can be performed in addition to the primary endpoint for a given sample. Where biopsy mass falls short, the primary endpoint will be prioritised.

§ Must be shown in at least 50% of evaluable participants.

Primary Objective	Primary Endpoint	How and when data is captured
To determine whether targeted release of doxorubicin from ThermoDox® ('drug') using mild hyperthermia generated non-invasively by focused ultrasound (FUS) is feasible in cancer patients	A demonstrable two-fold increase in*, or value exceeding 10µg/g of, the concentration of intra-tumoural doxorubicin at the treated tumour site following FUS-induced mild hyperthermia § Quantification of intra-tumoural drug release will be achieved by direct analysis of the intra-tumoural biopsy samples using standardised curve(s)	Analytical chemistry performed on a recorded mass of biopsy sample processed within 12 hours of intervention†

Table 1: Primary Objective and Endpoints for the TARDOX Study

Secondary Objectives	Secondary Endpoints	How and when data is captured
Part I only: To determine optimal FUS exposure parameters for a range of participant Body Mass Indices (BMIs) and tumour locations within the liver	Achievement of the desired range of mild hyperthermia in the target tissue as monitored by the implanted thermometry device during FUS exposure	Real-time thermometry monitoring during intervention
To assess the safety of FUS-induced mild hyperthermia for drug delivery	1. Persistence of cell viability stain or percentage of cell or tissue necrosis under 30% following FUS exposure, as assessed by cytological or histological	1. Cytological or histological analysis of biopsy samples processed within 96hr of intervention†

	methods ¹⁶ ‡,§ 2. Adverse events deemed related to FUS up to 30 days post-intervention	2. Adverse event recording for 30 days post-intervention
To assess the local and systemic cytotoxic effects of ThermoDox® in this setting	1. Significant bone marrow suppression, deranged liver function and liver toxicity 2. Adverse events deemed related to ThermoDox® up to 30 days post-intervention	1. Grade 3 and 4 laboratory results from blood tests at Day 1 and Day 15 post intervention 2. Adverse event recording for 30 days post-intervention

Table 2: Secondary Objectives and Endpoints for Parts I & II of the TARDOX Study

Regarding participants for which doxorubicin has been released by optimal FUS exposure parameters:

Tertiary (Exploratory) Objectives	Tertiary (Exploratory) Endpoints	How and when data is captured
1. To establish the validity of other minimally-invasive and non-invasive methods of evaluating intratumoural uptake of doxorubicin as an alternative to that used in primary endpoint	Combined analysis of relevant end points to establish most effective alternative analytical method(s) for quantifying drug release	See below
a. Fluorescence microscopy of biopsy	Released biopsy samples exhibiting regions of nuclear or background fluorescence levels at least twice that of a suitable control, as assessed by fluorescence microscopy ‡,§	Microscopic analysis of biopsy samples processed within 96hr of intervention†
b. MR-Spectroscopy	Liver MRI/MR-Spectroscopy indicating ¹⁷ targeted delivery of doxorubicin to the tumour by demonstrating a statistically significant increase in the tumour:background ratio of signal intensity following intervention compared to baseline	MRI/MR-Spectroscopy signal within 36 hours of intervention
c. Plasma pharmacokinetics	A statistically significant decrease in total doxorubicin plasma levels over time-matched clearance levels, following HIFU-induced release	Analytical chemistry of plasma samples processed within 12hr of intervention†
2. To determine whether the dose of doxorubicin released has a therapeutically significant effect on the target tumour	Radiological evidence of tumour response at timepoints over 30 up to 60 days in the FUS-targeted tumour and control(s), as assessed by principles of Choi and RECIST response evaluation using MRI and CT [11, 12] and SUV _{max} using PET-CT [13] §	Scans to be performed within 60 days of intervention.

Table 3: Tertiary (Exploratory) Objectives and Endpoints for Parts I & II of the TARDOX Study

¹⁶ In some necrotic tumours, base line necrosis may be high (e.g. >30%) even prior to treatment. Consequently an increase in necrosis by no more than 25% over that of a suitable control can be used as an alternative endpoint.

¹⁷ The spectroscopy signal analysed may not be doxorubicin itself; metabolites or breakdown products of ThermoDox® may be utilized.

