Primary Endpoint:	A demonstrable two-fold increase in, or value exceeding 10µg/g of, the concentration of intra-tumoural doxorubicin at the treated tumour site following FUS-induced mild hyperthermia, in at least 50% of evaluable participants.
Secondary Endpoints:	
 Part I only: Achievement of the desired range of mild hyperthermia in the target tissue as monitored by the implanted thermometry device during FUS exposure

	
 2. Persistence of cell viability stain or percentage of cell or tissue necrosis under 30% following FUS exposure, as assessed by cytological or histological methods 3. Significant bone marrow suppression, deranged liver function and liver toxicity. 4. Adverse events up to 30 days post-intervention: 
 a. Deemed related to ThermoDox® b. Deemed related to FUS
Tertiary (Exploratory) Endpoints:	
Regarding doxorubicin released by optimal FUS exposure parameters:
 
 1. Combined analysis of relevant end points to establish most effective alternative analytical method(s) for quantifying drug release: 
 a. Released biopsy samples exhibiting averaged regions of nuclear or background fluorescence levels at least twice that of a suitable control, as assessed by fluorescence microscopy b. Liver MRI/MR-Spectroscopy indicating targeted delivery of doxorubicin to the tumour by demonstrating a statistically significant increase in the tumour:background ratio of signal intensity following intervention compared to baseline c. A significant decrease of in total doxorubicin plasma levels over time-matched clearance levels, following FUS-induced release 2. Radiological evidence of tumour response at timepoints up to 60 days post-intervention in the FUS-targeted tumour and control(s), as assessed by Principles of Choi and RECIST response evaluation using MRI and CT [11, 12] and SUV_{max} using PET-CT [13]

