5.1.3.1 Ultrasound Screening Assessment

A focused diagnostic ultrasound scan will be performed in order to choose suitable tumour area(s), which are easily identified on ultrasound and amenable for biopsy. For participants in both Parts I and II, a single liver tumour amenable to intervention will be targeted. The tumour selected for intervention will be treated with a combination of ThermoDox® and FUS. Refer to section 5.4.3 for more information on the FUS intervention.

As assessed at the Ultrasound session, in order to proceed with the study, the participant must:

1. Have one or more incurable (unresectable, non-ablatable-for cure) liver tumours of size 1cm or greater, which is amenable to ultrasound-guided biopsy
2. Have the total volume to be treated no larger than either removal of 3 hepatic segments or removal of more than 30% of total liver volume (as per maximum surgical limit)
3. Be an appropriate candidate for FUS with consideration given to the following factors:
 - a. Overall health of liver
 - b. Absence of significant cirrhosis
 - c. Absence of significant ascites
 - d. Ultrasound path free of previous radiotherapy or scar tissue
 - e. Ultrasound path free of overlying skin ulceration

In some circumstances, if a participant is found to be ineligible for Part I of the study due to anatomical tumour location, they may still be eligible for Part II. This is because real-time temperature monitoring is not required in Part II and thus the anatomical position of a given tumour area may be more amenable to delivery of the intervention.

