- A Pre-Treatment Biopsy of the tumour is taken via the co-axial needle, and used as a baseline prior to any intervention, along with the Pre-Treatment blood sample.
- A clinically approved thermometry device is then positioned through the co-axial needle to the target area and is used to obtain real-time thermometry measurements during the FUS exposure.
- The HIFU therapeutic device is aligned to the thermometry device using short test exposures of FUS.

- The tumour area is then exposed to varied and considered FUS parameters (section 5.4.3) until the thermometry confirms that the target range of mild hyperthermia has been achieved within the tumour(*).
- In addition to the FUS exposure parameters (power (watts), duty cycle, duration of treatment) and associated thermometry data, the location of tumour (liver segment) and patient BMI will be recorded for each intervention.
- The thermometry device is then replaced and a cool-down period allows the tumour to return to body temperature.
- Once the tumour has returned to normothermia, the prescribed dose of ThermoDox® is infused over a duration of 30 minutes.
- A second Unreleased Drug Biopsy of the target area is then taken via the coaxial needle (Note: ThermoDox® is circulating at this point, but not yet activated). The corresponding Unreleased Drug blood sample is also taken at this stage for pharmacokinetic analysis within 15 minutes of infusion end.
- The tumour area is then re-exposed to FUS using the exposure parameters identified earlier as being suitable to generate mild hyperthermia within the tumour. During this second FUS exposure, ThermoDox® is circulating between therapeutic and peak levels.
- After completion of the final FUS exposure, a final Released Drug biopsy is taken via the co-axial needle with the corresponding Released Drug blood sample.
- Before removing the coaxial needle, a Gelfoam® (or equivalent) plug embolization of the needle track is applied through the needle to minimise bleeding risk [47].

*Note that with increasing experience, the study team may elect to omit the step of pre-heating the tumour prior to drug delivery (1st FUS exposure) and drug infusion may be commenced shortly after alignment.

The steps of intervention of the liver tumour in Part I are summarised in Figure 4.

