The paired Pre-treatment, Unreleased and Released Drug samples (bloods and biopsies) are sent for analysis in an appropriate laboratory. Please refer to section 7 for more information on sample analysis.

[figure not shown]

Figure 4: Timeline for combination exposure of the target liver tumour in Part I (not to scale, total plasma doxorubicin PK curve is for illustrative purposes to demonstrate anticipated PK trend and is not based on actual PK data)

Part II

The optimised FUS acoustic parameters for Part I will be used in Part II. The release of doxorubicin and its therapeutic effect will be investigated. The PI or delegate will have already identified a suitable solitary target liver tumour for intervention at the Ultrasound Session (section 5.1.3.1).

Day 1 (Intervention):

- Preparation as for Part I with the exception that no real-time thermometry data acquisition or pre-intervention biopsies are required in Part II, thus the co-axial needle for biopsy can be inserted after the FUS exposure. Three peripheral blood samples for plasma analysis are taken at the corresponding stages of the intervention (Pre-treatment, Unreleased and Released) as for Part I. The time the blood and biopsy samples are taken must be noted.
- ThermoDox® is infused as per prescribed dose for a duration of 30 minutes.
- After the infusion, the lesion identified for intervention (ThermoDox® release by mild hyperthermia) is exposed to the planned FUS exposure dose, as optimised in Part I, taking into consideration the patient BMI and tumour location (section 5.4.3).
- The non-FUS control tumour, if available, is exposed to ThermoDox® alone without FUS.
- As for Part I, the FUS exposure parameters, location of tumour (liver segment) and patient BMI will be recorded for each evaluation.
- The co-axial needle is inserted and up to two ultrasound-guided Released Drug Biopsies of the tumour receiving intervention are taken, whilst the participant is still under General Anaesthetic. A biopsy is not taken of the control tumour exposed to ThermoDox® only. A corresponding Released Drug blood sample is also taken.
- Before removing the coaxial needle, a Gelfoam® (or equivalent) plug embolization of the needle track is applied through the needle to minimise bleeding risk [47].

The steps of intervention for the liver tumour in Part II are summarised in Figure 5.

[figure not shown]

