17.2 Subgroup analysis

No subgroup analyses are planned for the study.

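### Primary success can be reached without a rise over the participant's own pre-FUS drug level, and paired and unpaired successes are pooled under one 50% rule

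*Protocol*

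**What the plan says.** - **Endpoint.** Section 3, Table 1 defines success as "A demonstrable two-fold increase in*, or value exceeding 10µg/g of, the concentration of intra-tumoural doxorubicin at the treated tumour site". It must be shown in at least half of evaluable participants. The synopsis gives the same two alternatives.
- **Part I comparator.** Section 5.4.2 has a core taken after the infusion and before the final FUS exposure: "A second Unreleased Drug Biopsy of the target area is then taken via the coaxial needle". Each Part I participant therefore has an own Unreleased value.
- **Part II comparator.** Section 5.4.2 states that "no real-time thermometry data acquisition or pre-intervention biopsies are required in Part II". Under qualifier * in section 3, "the average value for all evaluable tumours receiving intervention in Part I is used as a comparison for the two-fold increase".
- **Who enters which Part.** Section 2 lets Part II open after the Trial Management Group has reviewed at least 5 thermometry participants. Section 17.3 keeps Part I open in parallel and lets clinicians choose the Part partly by tumour location. Section 5.1.3.1 adds that a patient may be "ineligible for Part I of the study due to anatomical tumour location, they may still be eligible for Part II".
- **Pooling.** Section 2 puts all evaluable participants of both Parts into the endpoint analysis, up to 28 (section 16.1). Section 17.2 says: "No subgroup analyses are planned for the study".

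**The concern.** The primary objective is whether FUS releases drug in the tumour. The comparison that isolates this is Released against Unreleased in the same tumour, with drug already circulating in both samples. Two features of the endpoint give up that control but count equally.

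1. **The absolute route ignores the pre-FUS level.** A Part I participant with Unreleased 12 and Released 11 µg/g is a success for targeted release, although the level fell and the paired core shows it.
2. **The Part II two-fold route uses other people's unheated level.** The result mixes the FUS effect with differences in uptake between patients. Every Part II participant is also judged against the same mean, which may rest on few tumours in patients not randomly allocated to Part I.

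The headline proportion then adds paired, borrowed and absolute successes together. A reader could not tell how many of them show a rise. The pooled result could overstate release if unheated levels are near 10 µg/g, or understate it if they are low and vary between patients.

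**Working it through.** **Plan's own figure.** There is none to reproduce. Section 16.1 gives only a maximum of 28 evaluable participants, with no null rate, effect size or SD. At 28 the rule means at least 14 successes.

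**Step 1, the absolute route on its face.** With Unreleased 12 and Released 11, the ratio is 11/12 = 0.92, so the two-fold route fails. But 11 > 10, so the participant succeeds.

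**Step 2, model for the two-fold route.** These assumptions are not in the protocol: Unreleased = exp(b + e₁), Released = fold × exp(b + e₂), log-SD of b 0.7 (between patients), log-SD of e 0.4 (within patients). The Part I/Part II split is 5/23 or 14/14. The protocol's average is read as the arithmetic mean.

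*Part I, own comparator.* P(success) = Φ[(ln fold − ln 2)/(0.4√2)].
- Three-fold: Φ(0.405/0.566) = Φ(0.72) = 0.76.
- No effect: Φ(−0.693/0.566) = Φ(−1.22) = 0.11.

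*Part II, borrowed comparator.* The Released log-SD is √(0.49 + 0.16) = 0.806. The arithmetic mean of Unreleased lies above the median by a log amount of 0.65/2 = 0.325. With a very large Part I, a three-fold effect gives Φ[(0.405 − 0.325)/0.806] = Φ(0.10) = 0.54. For a finite Part I the mean is itself random, so simulation is needed (40,000 trials per setting):

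| Two-fold route only | 5/23 | 14/14 |
|---|---|---|
| Part I success, true three-fold | 76% | 76% |
| Part II success, true three-fold | 57% | 55% |
| Variance of Part II rate ÷ binomial variance, three-fold | about 3.7 | about 1.7 |
| P(at least 14/28), no effect | about 1% | about 0 |

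At 5/23 and three-fold, the Part II rate has SD 0.200 against a binomial 0.103, and its 5th–95th percentile range is 22–87%. For between-patient log-SD 0.5 to 0.9, Part II success runs from 64% to 52%. With no effect at 5/23, Part II success is 15% against 11% in Part I.

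*Trial level, three-fold effect, 5/23.* The two-fold route reaches 14/28 in 84%, 75% and 67% of trials for between-patient log-SD 0.5, 0.7 and 0.9.

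**Step 3, both routes, no FUS effect, 5/23.** The 10 µg/g threshold needs an unheated level, which the protocol does not give. With the same SDs:

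| Assumed unheated median (µg/g) | P(at least 14/28) |
|---|---|
| 5 | about 1% |
| 8 | 19% |
| 11 | 77% |

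A second parameter set (within-patient log-SD 0.3, between 0.3 to 0.9, both splits) gives 0–1.5% at 5, 2–24% at 8 and 75–88% at 11.

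**Step 4, agreement.** Under that second set, own and borrowed comparators classify the same Part II participant alike in only 54–77% of cases when the true rise is two- to three-fold.

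**The case against.** The strongest reply is that the borrowed comparator is disclosed and deliberate. This is a Phase 1 feasibility study, and Part II omits the earlier biopsies so as to resemble practice. The borrowed mean seldom creates a false claim by itself, and the 5/23 split is an extreme, because 5 is a minimum and Part I stays open. The absolute route matters only if unheated tumour levels approach 10 µg/g, which nothing in the protocol shows. All of this stands, and it limits the severity. It does not remove the fact that a stated rule counts a falling level as release.

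Several stronger readings are tempting but not supported:

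- **That the comparator keeps moving while Part I recruits.** Sections 3 and 17.3 put endpoint evaluation at the end, so the mean can be computed once. A longer Part I only enlarges it.
- **That the pooled proportion is the only planned result.** Section 12 also plans a statistical comparison of Unreleased with Released biopsies. Within participants, only Part I can supply it. That test does not change the primary definition.
- **That the planned interval is too narrow.** The protocol states no interval or test for the proportion. The variance ratio is a warning for whoever chooses one.
- **That the assay counts liposomal drug in blood.** The protocol does not say so, and the point does not need it.
- **That Section 17.2 forbids a table by Part.** The Parts are design stages. The protocol does not require such a table, but it does not clearly bar one.

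**Conclusion.** The point holds as a defect in how the primary endpoint is defined and reported, at should-fix level. The text establishes that the absolute route is unconditional, that the Part II two-fold route is unpaired, and that both are pooled with paired Part I results under one threshold.

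A reader might infer that the endpoint always favours success, but it does not. Under the assumed SDs, the borrowed mean mainly hides a real effect (76% against 55–57% at three-fold). With no effect it gives trial success in about 1% of trials or fewer. The absolute route can only add successes. Its harm is negligible at an unheated median well below 10 µg/g and decisive near or above 10. The Part I Unreleased cores will show which case applies.

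All percentages rest on assumed SDs, splits and unheated levels. The Part I/Part II comparison and the variance ratios cover the two-fold route alone.

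**What to change.** - Keep the pooled proportion. Beside it, report primary success separately for Part I and Part II, and by route: own two-fold, borrowed two-fold, and above 10 µg/g only.
- Rest any statement that FUS released drug on the paired Part I result.
- In Part I, count the above-10 route only if Released exceeds the participant's own Unreleased value and that Unreleased value is not itself above 10 µg/g.
- Report how many Part I Unreleased cores exceed 10 µg/g. This shows directly how often the threshold is passed before the final FUS exposure.
- If an interval is given for Part II or the pooled proportion, obtain it by a method that also resamples the Part I Unreleased values.
- Keep the arithmetic mean as the Part II comparator and use the geometric mean only as a sensitivity analysis. It is a trade-off: in the no-effect model at 5/23 it raises Part II success from 15% to 22%.

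The cost is wording and a small amount of analysis, with no extra biopsies or participants. The price is that the release claim rests on fewer participants, with wider intervals. Because Part II has no own Unreleased value, the condition on the absolute route can apply only in Part I, which is a further reason to show the Parts separately.
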